#### **6.2.5 Electrocardiograms**

A 12-lead ECG will be done at baseline, Week 52, and at the End of Treatment visit. Baseline and Week 52 ECGs (and early termination visits occurring in the first year) will be done at the study center on the same model unit. The end of treatment ECG may be done locally. Recorded data will include general findings, ventricular rate (bpm) and P-R, QRS, and QTc intervals (seconds). Any ECG abnormalities, as determined by the investigator, at screening will be recorded as medical history. Any clinically significant adverse change from the status at the screening visit and noted to be clinically significant by the investigator should be captured as an

AE. All ECGs conducted during the first year of the study will be assessed by a central reader and this assessment will be used as the primary data readout for the study. However, investigators are also responsible for providing their own interpretation of the ECG, and this will be captured on the ECG print out. Two copies of the ECG tracings should be retained in the subject source record. The local, end of treatment ECG will not be sent to the central reader, unless necessary in order to confirm an ambiguous result or serious abnormality.

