**Table 6-3 Schedule of Evaluations and Procedures – Long-term Extension after Month 36**

Study Procedures	Proposed Study Month a	Months 38/50/62	Months 40/52/64	Months 42/54/66/74	Months 44/56/68/76	Months 46/58/70/78	Months 48/60/72/80	End of Treatment b	4 weeks F/up Phone c
	Visit Windows	± 2 weeks	± 2 weeks	± 2 weeks	± 2 weeks	± 2 weeks	± 2 weeks	± 1 week	± 7 days

a Study visits will be conducted every 2 months and will continue until the subject voluntarily withdraws or until termination of the study. At that time, and periodically following that milestone, the study will be reviewed in regard to continuation/termination status.

b After the End of Treatment visit or early termination visit, subjects who will not continue rhPTH[1-84] treatment will have their total serum calcium and phosphate levels measured 3 to 5 days after the last dose of study medication. Doses of calcium and active vitamin D supplements will be adjusted by the Investigator as appropriate. Thereafter, the Investigator will repeat serum calcium/phosphate monitoring and supplement dose adjustments as appropriate to achieve target serum calcium/phosphate concentrations until the follow up phone call 4 weeks ± 7 days after end of treatment visit. After the 4 week follow up phone call, further management of hypoparathyroidism will occur as part of the subject's long-term non-study medical care.

c Follow-up phone contact 4 weeks after the last dose of study medication to check on any ongoing or new drug-related AEs or SAEs

d Study subjects must be re-consented at their next study visit prior to implementation of Amendment 6.

e Brief physical exams will be conducted at 6-month intervals.

f Vital signs should be done prior to blood draws.

g The End of Treatment ECG will be read locally.

h Calcium supplements should be withheld for 24 hours prior to the DXA scan. If a subject cannot withhold the calcium supplements due to safety concern, the DXA should be performed 2 hours after the last calcium tablet has been ingested.

i DXA will be performed at End of Treatment visit ONLY if the previous DXA was ≥3 months prior.

j Fasting for at least 6 to 8 hours prior to test

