3.3. Determination of Sample Size

Approximately 50 subjects are anticipated to be enrolled. This sample size is based on an estimate of the number of subjects who potentially could roll over from RELAY and/or REPLACE study and is not calculated based on the statistical assumptions.

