5.1. General Methodology

All statistical procedures will be completed using SAS version 9.4¹. No formal statistical testing will be conducted for this study. Summary statistics will be provided.

Continuous variables, including those assessed on a discrete scale, will be summarized using descriptive statistics including number of subjects, mean, median, standard deviation, maximum, and minimum. For categorical variables, statistical summaries will include number of subjects and percentages.

For summary purposes, baseline will be defined as the last available pre-dose value, unless otherwise specified. End of treatment (EOT) time point, defined as the last determination of response or last available measurement during the treatment period (from the date of first dose to the date of last dose + 1 day), will be analyzed in addition to the scheduled visits. Visits will be summarized based on the analysis visit windows.

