6.8.3. ECG Evaluations

The number and percentage of subjects with each type of ECG finding (Normal/Abnormal, Not Clinically Significant/Abnormal, and Clinically Significant) will be presented by visit.

Actual value and change from baseline for each ECG parameters (HR, PR, QRS, QT, QTcB, QTcF) will be presented by visit.

Potentially clinically significant QTc finding criteria are defined in Table 7. The number and percentage of subjects with post-baseline results qualifying as potentially significant will be summarized by parameter. A listing will present all values for a subject and parameter for cases where at least one value for that parameter was potentially significant.

Table 6.3 Potentially Clinically Significant Post-Baseline ECG^{5,6}

ECG Parameter	Potentially Clinical Significant Criterion
QTcB	≥ 500 ms
QTcF	≥ 500 ms
QTcB	An increase from Baseline of ≥ 60 ms or ≥ 30 ms
QTcF	An increase from Baseline of ≥ 60 ms or ≥ 30 ms

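### The QTc change criterion in SAP Table 6.3 joins 60 ms and 30 ms with 'or', so it reduces to 30 ms and no count at 60 ms is required

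*SAP*

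**What the plan says.** SAP 6.8.3, Table 6.3, has four rows. Two are absolute limits of 500 ms, one for QTcB and one for QTcF. The other two, again one per correction, are the change criterion: "An increase from Baseline of ≥ 60 ms or ≥ 30 ms". The reporting rule is "The number and percentage of subjects with post-baseline results qualifying as potentially significant will be summarized by parameter".

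The same section plans two other outputs that bear on the point. One is a listing: "A listing will present all values for a subject and parameter for cases where at least one value for that parameter was potentially significant". The other is a by-visit summary: "Actual value and change from baseline for each ECG parameters (HR, PR, QRS, QT, QTcB, QTcF) will be presented by visit". Under SAP 5.1, continuous variables are summarized with "descriptive statistics including number of subjects, mean, median, standard deviation, maximum, and minimum".

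On size and timing, SAP 3.3 says "Approximately 50 subjects are anticipated to be enrolled", and Protocol 6.2.5 says "A 12-lead ECG will be done at baseline, Week 52, and at the End of Treatment visit". Year-1 ECGs are read centrally, but a footnote to Protocol Table 6-3 says "The End of Treatment ECG will be read locally". SAP 8 defers table layouts to a separate mock-table document that is not available here.

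**The concern.** Joining two nested thresholds with 'or' makes the higher one idle. A programmer who follows the text literally flags every rise of at least 30 ms and produces one figure for QTcB and one for QTcF. Rises of 31 ms and 65 ms then fall in the same count.

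The SAP says so when it wants graded reporting. Adverse events are summarized by any and by highest category of severity and relationship (SAP 6.8.1), and creatinine clearance is summarized by stage (SAP 6.8.2, Table 6.1). Section 6.8.3 has no such wording for QTc.

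This matters more here than in many trials. Long-term safety is the primary objective (SAP 2.1) and ECG parameters are a listed safety endpoint (SAP 4.5). There is no control arm, no formal testing and no DSMB (SAP 5.1, 5.5), so descriptive counts carry much of the interpretation. Small QTc differences are also hard to read in this design. For most subjects the baseline comes from an earlier study (SAP 5.3.2), and the End of Treatment ECG may be recorded and read locally, up to 80 months into treatment (Protocol 3.2, 6.2.5).

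**Working it through.** The plan states no expected number of QTc outliers, so there is no figure to reproduce. Two checks apply.

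**1. Logic.** Let d be the change from baseline in ms. The rule flags d if d ≥ 60 or d ≥ 30. Because d ≥ 60 implies d ≥ 30, the rule flags exactly the set d ≥ 30. A check over every integer d from −100 to 199 found no exception.

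**2. How many flags chance alone would give at each threshold.**

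Inputs from the documents:
- N = 50 subjects (SAP 3.3)
- two scheduled post-baseline ECGs per subject, at Week 52 and End of Treatment (Protocol 6.2.5)
- thresholds c = 30 and c = 60 ms (SAP Table 6.3)

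Assumptions, because the documents give no figures:
- no true change in QTc
- normally distributed changes with SD s, shown for 10 to 25 ms
- all 50 subjects contribute both ECGs
- correlation 0.5 between the two changes, because they share one baseline value (this follows if the three readings have equal, independent errors)

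Formulas:
- one ECG: p1 = 1 − Φ(c/s)
- either of two ECGs: p2 = 1 − P(Z1 < c/s and Z2 < c/s), with Z1 and Z2 bivariate standard normal, correlation 0.5
- expected subjects flagged: 50 × p2

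Worked case, s = 15 and c = 30: c/s = 2, p1 = 0.02275, p2 = 0.04145, and 50 × 0.04145 = 2.07.

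| SD of change (ms) | p1 at ≥30 | p2 at ≥30 | Expected of 50 at ≥30 | p2 at ≥60 | Expected of 50 at ≥60 |
|---|---|---|---|---|---|
| 10 | 0.00135 | 0.00262 | 0.13 | 0.00000 | 0.00 |
| 12 | 0.00621 | 0.01175 | 0.59 | 0.00000 | 0.00 |
| 15 | 0.02275 | 0.04145 | 2.07 | 0.00006 | 0.00 |
| 20 | 0.06681 | 0.11529 | 5.76 | 0.00262 | 0.13 |
| 25 | 0.11507 | 0.19059 | 9.53 | 0.01541 | 0.77 |

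The chance of at least one flag at ≥30 ms is 1 − (1 − p2)^50. It is 12% at SD 10, 88% at SD 15 and 99.8% at SD 20. An expected count of one or more at ≥30 ms needs an SD of about 13.0 ms with two ECGs, or 14.6 ms with one.

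The correlation matters little. Treating the two changes as independent gives 50 × [1 − (1 − 0.02275)²] = 2.2 at SD 15 and 50 × [1 − (1 − 0.06681)²] = 6.5 at SD 20.

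**The case against.** The strongest reply has four parts.

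- **Shorthand.** An author who wanted only 30 ms had no reason to write 60, so the row may mean two reporting categories that the mock tables separate. That is plausible and cannot be ruled out. But the SAP text does not say it, and the SAP is the controlling document.
- **The data stay visible.** A reader might infer that serious QTc findings would be hidden. The documents do not support that. Any subject with a 60 ms rise is flagged, so all that subject's values for the parameter are listed, and the by-visit summaries print the largest value and the largest change. Clinically significant ECG changes are also captured as adverse events (Protocol 6.2.5). With about 50 subjects the listing is short. This part stands in full, with one limit: a maximum shows that an extreme value exists, not how many subjects had one.
- **The 500 ms limit.** A reader might also infer that values of 500 ms or more are merged into the same count. That limit has its own row for each correction. A count by parameter could pool the rows, but nothing says that it does. The point is unclear, not established.
- **Chance flags.** It is tempting to say that the reported count is what noise alone would produce. That depends on an SD the documents do not give. It is true at about 13 ms or more with two ECGs and false at 10 ms. The earlier-study baseline and the local End of Treatment reading make a larger SD plausible but supply no figure.

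The reply also notes that no decision rule hangs on this count and that the thresholds can be tabulated later from data already collected. That is right. It limits the consequence but does not repair the rule.

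**Conclusion.** Wrong as written. The change criterion for QTcB and QTcF is logically identical to ≥30 ms. With counts by parameter, the SAP requires no n (%) at ≥60 ms and can pool 60 ms rises with 30 ms rises. This rests on the text alone.

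The loss is a tabulated count, not the underlying data. Its practical size depends on the assumed SD of QTc change. At 15 to 20 ms, about 2 to 6 of 50 subjects would be flagged at ≥30 ms with no drug effect, against 0.00 to 0.13 at ≥60 ms, so the higher threshold would be the informative one. At 10 ms the ≥30 ms count would itself be nearly free of chance flags (0.13 of 50), and the gain from separating the two would be small. These figures also assume normal changes and both ECGs from every subject.

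**What to change.** In SAP Table 6.3, replace the change row for each of QTcB and QTcF with two exclusive rows: increase ≥30 to <60 ms, and increase ≥60 ms. Class each subject by the largest post-baseline increase. Keep ≥500 ms as its own row. Change the reporting sentence in Section 6.8.3 so that n (%) is summarized by parameter and criterion. While there, correct the cross-reference: the section points to Table 7, but the table is numbered 6.3.

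The cost is one split row per correction in the SAP and the matching change in the mock tables. No new data are needed, and study conduct does not change.

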6.8.4. Vital Signs, Physical Findings, and Other Observations Related to Safety

In general, other by-visit safety findings will be analyzed and presented in a way similar to laboratory variables.

6.8.4.1. Vital Signs

Vital signs to be analyzed include sitting blood pressure, sitting heart rate, and body temperature.

Observed vital signs and changes from baseline will be summarized by visit.

The number and percentage of subjects with post-baseline results qualifying as markedly abnormal will be summarized by parameter. A listing will present all values for a subject and parameter for cases where at least one value for that parameter was markedly abnormal. Post-baseline markedly abnormal vital signs criteria are defined in Table 8.

Table 6.4 Markedly Abnormal Post-Baseline Vital Signs⁷

Vital Sign Parameter	Abnormally Low	Abnormally High
Systolic blood pressure (mmHg)	A decrease from Baseline of ≥ 20 to a value ≤ 90	An increase from Baseline of ≥ 20 to a value ≥ 180
Diastolic blood pressure (mmHg)	A decrease from Baseline of ≥ 15 to a value ≤ 50	An increase from Baseline of ≥ 15 to a value ≥ 105
Heart Rate (bpm)	A decrease from Baseline of ≥ 15 to a value ≤ 50	An increase from Baseline of ≥ 15 to a value ≥ 120
Temperature ($^{\circ}\text{C}$)	N/A	Value $\geq 38.3^{\circ}\text{C}$ and $\geq 0.8^{\circ}\text{C}$ increase from Baseline

6.8.4.2. Body Weight

The observed values and changes from baseline for body weight and BMI will be summarized at each visit.

6.8.4.3. Serum 25-Hydroxyvitamin D and Serum 1,25-dihydroxyvitamin D

The observed value and change from baseline in serum vitamin D levels (Serum 25-hydroxyvitamin D and Serum 1,25 vitamin D) will be summarized descriptively by visit.

6.8.4.4. Physical Examination Findings

Physical examination results will be presented in appendix data listings only.

6.8.4.5. PTH and ECP Antibodies

The number and percentage of subjects classified as having antibodies to PTH and ECP at baseline, Visit 5 (Week 24), Visit 7 (Week 40), and EOT will be tabulated for each treatment group.

If any subject tests positive for PTH-specific antibodies at the final visit, they will have follow-up blood draws for PTH antibody analysis at Months 2, 3, and 6 post-study. If a subject's results are negative at 2 successive visits within this timeframe, follow-up may be terminated. If at the end of 6 months the subject is still determined to have PTH-specific antibodies, the investigator and the sponsor will determine if additional follow-up may be required. During this time, subjects also will be evaluated for AEs or SAEs related to immunogenicity, which will be collected in the Pharmacovigilance database.

Subjects may remain on study if they develop PTH-specific antibodies during the study, providing that there are no concurrent AEs related to immunogenicity.

The number and percentage of subjects classified as having antibodies to PTH during the follow up period will also be provided, if applicable.

6.8.5. Concomitant Medications

Prior and concomitant medications will be coded to indication-specific ATC (Anatomic Therapeutic Chemical classification) and preferred name using the 1Q2010 version of the World Health Organization (WHO) Drug Dictionary.

Prior medications are defined as medications taken prior to the first dose of study medication in this study (RACE). Medications ongoing at the end of the previous study will be considered as prior medications. Concomitant medications are defined as medications that are taken during the treatment period of this study. Partial date imputation for medications is described in Section 7.4.3.

Prior and concomitant medication use will be summarized by level 2 ATC and preferred term using the number and percentage of subjects. Medications will be sorted alphabetically by ATC and preferred term within ATC. Subjects with multiple occurrences of a medication in ATC and preferred term will only be counted once within each ATC and preferred term. Since medications are coded to ATC by indication, preferred terms may appear under multiple ATCs.

7. Programming Conventions for Outputs

Partial dates should be presented as --NOV1999 or ---- 1999 as needed.

Partial times should be presented as --:30 or 14:-- as needed.

Listings should be sorted according to the order of the columns.

8. Mock Tables, Listings and Graphs (TLG)

The mock TLGs will be provided in a separate document and will follow the numbering scheme described in ICH, E3, Guideline for Industry, “Structure and Content of Clinical Study Reports” for tables, subject data listings and graphs.

9. References

1. SAS Institute, Inc. SAS OnlineDoc Version Eight. SAS Institute, Inc, Cary, NC, 1999.
2. Medical Dictionary for Regulatory Activities (MedDRA), Version 13.0. IFPMA, International Committee on Harmonization. Geneva, Switzerland. 2010.
3. National Kidney Foundation. Clinical Practice Guidelines for Chronic Kidney Disease: Evaluation, Classification, and Stratification. Part 4, Definition and Stages of Chronic Kidney Disease. [Updated 2000].
4. Data on File. ACM Global Central Laboratory April 2010.
5. FDA Guidance Industry on E14 Clinical Evaluation of QT/QTc Interval Prolongation and Proarrhythmic Potential for Non-Antiarrhythmic Drugs, October 2005; 9-11.
6. Data on File. ERT Cardiac Solutions 2012.
7. Prohealthsys.com Canada: Bates Physical Assessment and Web MD [updated 2010].

10. Appendix I: Summary of Changes Made to SAP version 1.0 Dated October 24, 2011

Changes that are editorial in nature (to correct typographical errors, errors in formatting, or to modify the language) are not included.

Section No.	SAP Version 1.0	SAP Amendment 1	Change Justification
Title	A 12-Month Open-label Study ...	A Long Term Open-label Study ...	In compliance to Protocol Amendment 3, Version 4.0
Section 5.1		Add a bullet 'At the end of Week 52, subjects will be invited to extend their study drug regimen until at least October 2013. During this time, subjects will return to the clinic for interim visits every 2 months (Months 14, 16, 18, etc).	In compliance to Protocol Amendment 3, Version 4.0
Section 5.1		Reordering of study visits to accommodate the long-term extension.	In compliance to Protocol Amendment 3, Version 4.0
Section 5.1	Figure 1	Replaced by Figure 1.1 and Figure 1.2	In compliance to Protocol Amendment 3, Version 4.0
Section 5.3	Approximately 40 subjects are anticipated to be enrolled.	Approximately 50 subjects are anticipated to be enrolled.	In compliance to Protocol Amendment 3, Version 4.0
Section 6.1	Table 1 Schedule of Study Evaluations and Procedures	Replaced by Table 1, Table 2, and Table 3	In compliance to Protocol Amendment 3, Version 4.0
Section 6.1		Add lab assessments 'Serum 1,25-dihydroxyvitamin D levels' and ECP antibody	In compliance to Protocol Amendment 3, Version 4.0
Section 6.2	Section header: Primary Efficacy Endpoint	Section header; Efficacy Endpoint	There is no primary efficacy endpoint defined in protocol.
Section 6.2	The proportion of subjects in whom the following three conditions are fulfilled at Week 52 (Visit 9):	The proportion of subjects in whom the following three conditions are fulfilled at Week 52 (Visit 9) and at the End of Treatment:	In compliance to Protocol Amendment 3, Version 4.0
Section 6.3	Section header: Secondary Efficacy Endpoints	Section header: Other Efficacy Endpoints	There is no secondary efficacy endpoints defined in protocol.
Section 7.5	An interim database with a cut off date of December 31, 2011 will be used to provide the NDA safety updates.	An interim study report will be completed to look at safety and efficacy compiled through 31 May 2013.	Project team decision.
